7 STUDY OBJECTIVES

7.1 Primary Objectives

The Primary objective of this pilot study is to establish safety and efficacy of a new enteric microgranule formulation of adrulipase in patients with EPI due to CF.

The primary safety objective of this study is to assess the safety and tolerability of the highest dose received of adrulipase (for subjects under Part 1, 1.2 g/day, 1.95 g/day or 2.4 g/day; for subjects under Part 2, 3.3 g/day) provided in size 00 capsules containing ~150 mg adrulipase. Efficacy will be evaluated by comparing CFA values during treatment with the highest dose of adrulipase versus baseline CFA obtained during screening of the patient's pre-study porcine PERT.

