5.1. Modified Intent-to-Treat Population

The modified intent-to-treat (mITT) population includes all enrolled patients receiving at least one dose of treatment and having at least one valid stool collection and CFA post baseline while receiving their assigned study drug.

A stool sample will be considered valid if the date and time associated with the second blue dye marker is recorded, indicating that the stool sample collection is complete.

The mITT population will be used for all analyses of efficacy endpoints.

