9.2.2. Primary Analysis of the Primary Endpoint

The primary analysis of the primary endpoint will be a comparison of the mean CFAs from the adrulipase treatment vs the PERT treatment (screening), using descriptive statistics. The primary efficacy endpoint analysis will use the mITT population. For the summary of CFA, if a subject switches back to PERT during the confinement period, prior to the end of the stool collection, then the CFA value will be excluded from the summary.

Values and change from baseline (Visit 2, on PERT) to end of treatment (Visit 6, on adrulipase) in stool weights will be summarized using descriptive statistics. Summaries will be performed for the overall group and by maximum dose of adrulipase received using descriptive statistics.

In addition, the number and percentage of subjects in the mITT population who have a CFA \geq 80% based on the CFA at week 6 (3-week post dose) will be summarized.

Fat consumed (g/24h), fat excreted (g/24h), and CFA (%) at each visit as well as CFA change from baseline to end of treatment will be listed for all subjects in the mITT population.

Details of each supervised confinement, including controlled diet and marker-to-marker stool collection, will be listed for all subjects in the mITT population.

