9.3.1. Stool Weight

Stool weight during the 72-hour marker-to-marker stool collections will be evaluated at Screening (Visit 2) and at the end of Treatment (Visit 6). All collected stool will be shipped to

the central lab for determination of the stool weight as described under the primary efficacy measure.

Stool weight will be analyzed from stool samples collected during the 2 scheduled confinements (Visit 2 and Visit 6).

Change from baseline (Visit 2, on PERT) to end of treatment (Visit 6, on adruclipase) in stool weights will be summarized using descriptive statistics. If a subject switches to PERT during the confinement period, prior to the end of the stool collection, then the stool weight value during that confinement period will be excluded from the summary.

If a subject has more than one stool weight record for a given visit (Visit 2 or Visit 6) and the correct value is unknown, only the heaviest value will be included in the summary.

Stool weight at each visit and change from baseline to end of treatment will be listed for all subjects in the mITT population.

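### SAP 9.2.2 drops the Visit 6 CFA of a patient who switches back to PERT but says nothing about that patient's Visit 2 CFA, so the two primary means can cover different patients

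*SAP*

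**What the plan says.** - **Objective.** Protocol 7.1: "Efficacy will be evaluated by comparing CFA values during treatment with the highest dose of adrulipase versus baseline CFA", with that baseline measured at screening on the patient's own PERT. SAP 3.1.1 has the same comparison.
- **Primary analysis.** SAP 9.2.2 specifies "a comparison of the mean CFAs from the adrulipase treatment vs the PERT treatment (screening"), by descriptive statistics. "The primary efficacy endpoint analysis will use the mITT population". Protocol 11.7.1 also asks for a comparison of means and has no switch-back rule.
- **Switch-back rule.** If a patient returns to PERT in confinement "prior to the end of the stool collection, then the CFA value will be excluded from the summary".
- **mITT entry.** SAP 5.1 requires at least one dose and "having at least one valid stool collection and CFA post baseline while receiving their assigned study drug". It then defines validity by the marker alone: "A stool sample will be considered valid if the date and time associated with the second blue dye marker is recorded".
- **Change from baseline.** The only sentence in SAP 9.2.2 that asks for values and change to be summarised names stool weights. CFA change is to be listed, not summarised. SAP 9.3.1 and 9.3.3 ask for a change summary for stool weight and for CNA.

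**The concern.** The trial's question is how each patient's CFA on adrulipase compares with that patient's CFA on PERT. Two means answer it only if they average the same patients. The switch-back rule removes one value and does not mention its partner. If the Visit 2 value stays in, the PERT mean has n = N and the adrulipase mean n = N − k, and their difference mixes the treatment contrast with a difference in who is averaged.

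Switching back is plausibly related to outcome. Protocol 6.6.3 reports that patients who left OPTION while on the study lipase did so mainly because of more EPI symptoms. CNA and stool weight have a summarised change, which needs both values. As written, the primary endpoint does not.

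**Working it through.** **Which reading do the texts support?**

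1. A switch back to PERT can occur only in the Visit 6 confinement, because at Visit 2 the patient is already on PERT. The single CFA value in the rule is therefore the Visit 6 value.
2. The parallel rule for stool weight (SAP 9.3.1) confines itself to one collection: "then the stool weight value during that confinement period will be excluded from the summary". That supports the same reading for CFA.
3. Is the switcher in mITT? By the marker definition, yes: Protocol 9.2.4.1 keeps patients confined until the second marker passes, so a switcher can complete a valid collection. By the on-drug clause of SAP 5.1, arguably no.
4. The analysis already uses mITT. If switchers were outside it, the exclusion rule in 9.2.2 would have nothing to act on. It has a purpose only if they are inside, which makes that the more natural reading.

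**How large can the mismatch be?**

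The plan has no figure to reproduce: SAP 3.4 states 12 patients without an SD, effect size or precision target.

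Inputs:
- N = 12 planned (SAP 3.4). Rows of 6 and 5 come from Protocol 6.7: six patients in Part 1, five of them dosed at 2.4 g/day when version 2.0 was written.
- Baseline CFA lies between 80% (inclusion criterion 6) and 100% (the most the CFA formula allows), a range of 20 points.
- k, the number of switchers, is not given. Assumed 1 to 3.

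Let m be the mean Visit 2 CFA of the N − k patients with a usable Visit 6 value, and b that of the switchers.

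PERT mean with switchers kept − PERT mean in matched patients = [(N − k)m + kb]/N − m = (k/N)(b − m)

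Since |b − m| ≤ 20, the shift is at most 20k/N.

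| N | k | Limit, 20k/N | If the baseline gap is 10 points |
|---|---|---|---|
| 12 | 1 | 1.67 | 0.83 |
| 12 | 2 | 3.33 | 1.67 |
| 12 | 3 | 5.0 | 2.5 |
| 6 | 1 | 3.33 | 1.67 |
| 5 | 1 | 4.0 | 2.0 |
| 5 | 2 | 8.0 | 4.0 |

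The limit needs switchers at one end of the range and everyone else at the other. With the others at 88 (assumed) and one switcher in 12, the shift is (80 − 88)/12 = −0.67 for a switcher at 80, and (97 − 88)/12 = +0.75 for one at 97, the OPTION maximum on PERT. The sign depends on the switcher's baseline.

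Worked example with assumed values: 11 patients at 88 on PERT and 60 on adrulipase, plus one switcher at 81 on PERT. With the switcher kept, the PERT mean is (11 × 88 + 81)/12 = 87.4 and the difference 60 − 87.4 = −27.4. In matched patients it is 60 − 88 = −28.0.

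**What pairing leaves untouched.** Dropping k Visit 6 values with mean x, when the others average a, raises the adrulipase mean by (k/N)(a − x). With a = 56 and x = 7 (OPTION mean and minimum, as illustration only), one dropped value gives 49/12 = 4.1 points in 12, or 49/5 = 9.8 in a row of five. With x = 40 (assumed), it gives 1.3 and 3.2.

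**The case against.** The strongest reply is the on-drug clause in SAP 5.1, which Protocol 11.3 shares. Visit 6 is the only post-baseline CFA. A patient who changed to PERT before the collection ended may have no qualifying value, would then leave mITT with both values, and the means would match. That reading is open. It makes the 9.2.2 rule redundant, which is why it is the less natural one.

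The stool-weight sentence in 9.2.2 also looks like a slip. It sits in the CFA section, stool weight has its own sentence in 9.3.1, and Protocol 11.7.2 says CNA is analysed as CFA is, while CNA gets values and change. A CFA change summary was probably intended. This stands as evidence of intent, but the text still needs correcting.

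Other points hold as well. The comparison of means comes from the protocol and was not introduced by the SAP. Counts accompany each summary and every mITT patient's CFA is listed, so with about 12 patients a reader could find the mismatch. The schedule places the return to PERT after the second marker, so k may be zero. No efficacy test is planned.

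A reader might infer more: that the SAP orders the Visit 2 value to be kept, that the headline difference is therefore wrong, and that the error favours adrulipase. The documents do not support this. The SAP never says the value is kept. OPTION's reasons for withdrawal bear on symptoms under the study lipase, not on switchers' CFA under PERT. It is also tempting to set the shift against the 6 points between OPTION's PERT mean (86%) and the 80% target, but neither document uses that gap as a margin.

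**Conclusion.** The point holds as an ambiguity with a limited consequence. On the more natural reading of SAP 5.1 and 9.2.2 together, a switcher with a completed collection is in mITT, contributes to the PERT mean and not to the adrulipase mean, and no summarised CFA change corrects for it. Two programmers could produce different headline means from the same data.

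The size is modest overall: at most 1.67 points for one switcher in 12, against the 30-point OPTION difference (86% − 56%). It grows in the small rows the plan reports: up to 3.33 points in six and 4.0 in five. In a row of one, a PERT mean would have no adrulipase counterpart. These limits rest only on the 80–100% baseline range, the row sizes and an assumed k. The direction cannot be determined in advance. Outcome-related loss of switchers' Visit 6 values may be the larger effect and is a separate matter.

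**What to change.** In SAP 9.2.2:

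1. Replace stool weights with CFA in the sentence on values and change from baseline.
2. State whether a switcher who completes the collection is in mITT, and align SAP 5.1 with the answer.
3. Compute both means and the mean within-patient change in mITT patients with an evaluable CFA at both Visit 2 and Visit 6, overall and within each dose or Part row. Show the common n.
4. List the Visit 2 and Visit 6 CFA of patients excluded for switch-back separately.

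The cost is a one-word correction, a few sentences and one filter in the table program. The PERT mean uses fewer patients when a switch-back occurs. Pairing does not address the selective loss of poorly controlled patients. SAP 9.2.4 covers only the CFA ≥ 80% summary and describes dropouts without a valid collection, so it does not say how a switcher with a completed collection is counted.

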9.2.3. Secondary Analyses of the Primary Endpoint

A secondary (supportive) descriptive summary of the primary efficacy measure will be provided using the per-protocol population.

9.2.4. Sensitivity Analyses of the Primary Endpoint (Best Case/Worst Case Scenarios)

The primary analysis is based on the mITT population which requires a post-baseline CFA. A subject could receive adrulipase but dropout without providing a valid stool collection for a CFA. Reasons for dropout could be related to lack of symptom control indicating a failure or could be due to reasons unrelated to treatment.

The descriptive summary of CFA \geq 80% (yes/no) at week 6 (3-week post dose) will be repeated in the safety population (1) assigning dropouts as 'yes' [best case scenario], and separately (2) assigning dropouts as 'no' [worst case scenario].

9.3. Secondary Endpoints

All secondary endpoint analyses except for the shift table of malabsorption signs and symptoms will be presented overall and by dose. Subjects are classified by maximum dose of adrulipase received during the study.

9.3.1. Stool Weight

Stool weight during the 72-hour marker-to-marker stool collections will be evaluated at Screening (Visit 2) and at the end of Treatment (Visit 6). All collected stool will be shipped to

the central lab for determination of the stool weight as described under the primary efficacy measure.

Stool weight will be analyzed from stool samples collected during the 2 scheduled confinements (Visit 2 and Visit 6).

Change from baseline (Visit 2, on PERT) to end of treatment (Visit 6, on adruclipase) in stool weights will be summarized using descriptive statistics. If a subject switches to PERT during the confinement period, prior to the end of the stool collection, then the stool weight value during that confinement period will be excluded from the summary.

If a subject has more than one stool weight record for a given visit (Visit 2 or Visit 6) and the correct value is unknown, only the heaviest value will be included in the summary.

Stool weight at each visit and change from baseline to end of treatment will be listed for all subjects in the mITT population.

9.3.2. Malabsorption signs and symptoms

Signs and symptoms of malabsorption will be evaluated at Visits 2, 3, 4, 5, 6, and 7.

The EPI malabsorption symptoms will be evaluated according to the following measures:

- Stool frequency (number of bowel movements per day);
- Stool consistency (graded as 0 = hard, 1 = formed/normal, 2 = soft, 3 = watery, or 4 = overt diarrhea);
- Bloating (graded as 0 = none, 1 = mild, 2 = moderate, or 3 = severe);
- Abdominal pain (graded as 0 = none, 1 = mild, 2 = moderate, or 3 = severe);
- Flatulence (graded as 0 = none, 1 = mild, 2 = moderate, or 3 = severe);
- Incidences of visible oil/grease in stool (Yes/No).
- Increased stool quantity (graded as 0 = none, 1 = mild, 2 = moderate, or 3 = severe); and
- Worsening of overall bowel habit (graded as 0 = none, 1 = mild, 2 = moderate, or 3 = severe).

Stool frequency will be summarized for the mITT population using descriptive statistics. Stool frequency will be summarized at Visit 2 (Screening, on PERT), At First Dose (Visit 3), 1 Week Post First Dose, 2 Weeks Post First Dose, 3 Weeks Post First Dose, and End of Study/Early Termination (Visit 7).

The number and percentage of subjects within each category for stool consistency, bloating, abdominal pain, flatulence, incidence of visible oil/grease in stool, increased stool quantity, and worsening of overall bowel habit at each study visit will also be provided at Visit 2 (Screening, on PERT), At First Dose (Visit 3), 1 Week Post First Dose, 2 Weeks Post First Dose, 3 Weeks Post First Dose, and End of Study/Early Termination (Visit 7).

Shifts from Visit 2 will be presented for stool consistency, bloating, abdominal pain, flatulence, increased stool quantity, and worsening of overall bowel habit for the mITT population. This shift table for malabsorption signs and symptoms will also be presented by whether a subject achieved CFA $\geq 80\%$ at 3 weeks post-dose (yes/no).

Signs and symptoms of malabsorption will be listed for all subjects in the mITT population.

9.3.3. Coefficient of Nitrogen Absorption

CNA at Screening (Visit 2, on PERT) and at the end of the 3-week treatment period (Visit 6, on adrulipase) will be analyzed.

CNA will be expressed as the percentage of nitrogen (protein) absorbed from the subject's diet.

CNA will be calculated using 2 data points:

- Nitrogen consumption in grams/24h (converted from fat consumption in grams/72h as provided by the qualified dietician at each site)
- Nitrogen excretion in grams/24h as provided by the central laboratory

CNA will be calculated as follows:

$$\frac{(\text{Grams/24h of nitrogen consumed} - \text{Grams/24h of nitrogen excreted}) \times 100}{\text{Grams/24h of nitrogen consumed}}$$

Values and change from baseline (Visit 2, on PERT) to end of treatment (Visit 6, on adrulipase) in CNA will be summarized using descriptive statistics. For the summary of CNA, if a subject switches back to PERT during the confinement period, prior to the end of the stool collection, then the CNA value will be excluded from the summary. Missing CNA values will not be imputed.

A secondary (supportive) descriptive summary of CNA will be provided using the per-protocol population.

Nitrogen consumed (g/24h), nitrogen excreted (g/24h), and CNA (%) at each visit as well as CNA change from baseline to end of treatment will be listed for all subjects in the mITT population.

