9.2.4 *Visit 7: End-of-Study /Early Termination Visit (Part 1 Day 28 ± 2 or Part 2 Day 21 ± 2)*

Patients will return to the clinic for their End of Study visit approximately 1 week after their last dose of study drug. If patients do not complete Visit 6, an Early Termination visit will be held approximately 1 week after the last dose of study drug. The procedures scheduled for the End-of-Study visit are the same as those that should be conducted for the Early Termination visit. The following procedures will be performed at the End-of-Study/Early Termination Visit:

- Focused physical exam to evaluate gastrointestinal tract, heart, and lungs
- Record any changes in AEs and concomitant medication
- Assess and record malabsorption signs and symptoms
- Collect a serum sample for circulating anti-adrulipase antibodies and adrulipase concentrations

- Perform a urine pregnancy test (urine dip stick), if applicable

9.2.4.1 *Instructions for Supervised Confinement for V2 and V6*

Dosing must have occurred for at least 16 days (Part 1) or 10 days (Part 2) prior to the supervised confinements. Beginning at breakfast (the first meal) on Day 1 of the supervised confinement, patients will be placed on a 72-hour controlled diet, with ~25 g fat/meal and 12.5 g fat/snack for a total of 100 g fat/day (3 meals and 2 snacks per day) and a minimum of 1.5 to 2 g of protein per kg of body weight. Although it is preferred to have the patient consume exactly 100 g of fat per day, the fat excretion assay remains valid with a fat intake range within 15% of the goal (i.e., 85 to 115 g of fat per day). The nutritional planning and calculation of dietary fat and nitrogen (protein) intake will be conducted by a qualified dietitian at each site. The actual fat and nitrogen (protein) intake will be calculated from the recorded type and amount of food consumed. A central laboratory will calculate CFA, CNA based on dietary intake and the fat and nitrogen excreted in stool. Stool weight values will also be recorded.

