2. PURPOSE OF THE ANALYSES

The statistical analysis plan (SAP) is being developed after review of the First Wave Biopharma, Inc. (First Wave), protocol number FWB-CF-2.03 (Version 1.0), but before any analyses of the data. The SAP contains detailed information to aid in the implementation of the statistical analyses and reporting of the study data for use in the clinical study report (CSR). This SAP is being written with due consideration of the recommendations outlined in the most recent International Conference on Harmonisation (ICH) E9 Guideline entitled Guidance for Industry: Statistical Principles for Clinical Trials and the most recent ICH E3 Guideline, entitled Guidance for Industry: Structure and Content of Clinical Study Reports.

This SAP describes the analysis sets that will be analyzed, the subject characteristics parameters, the efficacy parameters, and the safety parameters that will be evaluated. The details of the specific statistical methods that will be used will be provided in this SAP. If differences occur between analyses described in the SAP and the current protocol, those found in this SAP will assume primacy. If additional analyses are required to supplement the planned analyses described in this SAP, they may be completed and will be identified in the CSR. Table and listing specifications are provided in a separate document.

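### SAP 9.3.3 takes the nitrogen intake for CNA from fat consumption; a lesser slip in 9.2.2 names stool weights where CFA change is expected

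*SAP*

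**What the plan says.** **CNA intake.** SAP 9.3.3 builds CNA from two data points. Nitrogen excretion comes from the central laboratory. The intake term reads "Nitrogen consumption in grams/24h (converted from fat consumption in grams/72h as provided by the qualified dietician at each site"). The same section describes CNA as the share of dietary nitrogen (protein) absorbed, has nitrogen consumed in both numerator and denominator of its formula, and calls for a listing of "Nitrogen consumed (g/24h), nitrogen excreted (g/24h), and CNA (%) at each visit".

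Protocol 9.2.4.1 treats fat and nitrogen as separate quantities: "calculation of dietary fat and nitrogen (protein) intake will be conducted by a qualified dietitian at each site". It continues: "The actual fat and nitrogen (protein) intake will be calculated from the recorded type and amount of food consumed", and "A central laboratory will calculate CFA, CNA based on dietary intake and the fat and nitrogen excreted in stool".

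On precedence, SAP section 2 states: "If differences occur between analyses described in the SAP and the current protocol, those found in this SAP will assume primacy".

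**CFA change.** SAP 9.2.2, which sets out the primary analysis of CFA, contains this sentence: "Values and change from baseline (Visit 2, on PERT) to end of treatment (Visit 6, on adrulipase) in stool weights will be summarized". CFA change from baseline appears in 9.2.2 only as an item to be listed by patient. SAP section 2 adds that "Table and listing specifications are provided in a separate document".

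**The concern.** CNA is a named secondary endpoint, and 9.3.3 is where a programmer will look for its derivation. The only stated source of its intake term is the wrong nutrient. Correct output depends on someone overriding the written rule. The protocol wording does not formally repair it, because the SAP gives itself precedence where the two differ. If fat grams did reach the denominator, every CNA would be pushed towards 100% and any difference between adrulipase and PERT would be compressed.

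The 9.2.2 slip matters less. The efficacy objective (Protocol 7.1, SAP 3.1.1) compares each patient's CFA on adrulipase with that patient's baseline CFA on PERT. A descriptive summary of the paired change is the natural output, and the SAP text does not call for it.

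**Working it through.** The plan states no figure that depends on this rule, so there is nothing to reproduce. The finding rests on comparing the texts; the arithmetic only illustrates a possible size.

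**Texts side by side, CNA**

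| Place | Intake quantity |
|---|---|
| SAP 9.2.1, CFA data point | fat per 24 h, from fat per 72 h (correct) |
| SAP 9.3.3, CNA data point | nitrogen per 24 h, from fat per 72 h |
| SAP 9.3.3, definition, formula, listing | nitrogen |
| Protocol 9.2.4.1 | nitrogen (protein), from recorded food |

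The parenthesis in 9.3.3 repeats the one in 9.2.1, so it was very probably carried over when the CFA section was adapted. Neither document gives a conversion from fat to nitrogen.

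**Illustration: fat grams entered as nitrogen intake**

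Inputs from the documents:
- Mean CNA of 93% on the study drug and 97% on PERT (OPTION study, Protocol 6.6.3; an earlier formulation).
- Fat of 100 g/day, with 85 to 115 g accepted (Protocol 9.2.4.1).
- Protein of at least 1.5 to 2 g/kg (same section).

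Assumed, not in the documents: body weight 50 to 75 kg, 6.25 g protein per g nitrogen, and a central nitrogen intake of 16 g/day.

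Formula: apparent CNA = 100 × (1 − nitrogen excreted / fat consumed).

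1. Nitrogen excreted at a 16 g intake: 16 × 0.07 = 1.12 g (CNA 93%) and 16 × 0.03 = 0.48 g (CNA 97%).
2. Apparent CNA at 100 g fat: 100 × (1 − 1.12/100) = 98.88% and 100 × (1 − 0.48/100) = 99.52%.
3. Apparent difference: 99.52 − 98.88 = 0.64 point, against a true 4.0 points.
4. In general, apparent difference = 4 × nitrogen intake / fat intake.
5. Range of nitrogen intake: 50 × 1.5 / 6.25 = 12 g to 75 × 2 / 6.25 = 24 g.
6. At 100 g fat: 4 × 12/100 = 0.48 to 4 × 24/100 = 0.96.
7. Over the accepted fat range: 4 × 12/115 = 0.42 to 4 × 24/85 = 1.13.

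Wider assumptions (50 to 80 kg; 5.7 to 6.4 g protein per g nitrogen) give nitrogen intakes of about 12 to 28 g and a difference of about 0.5 to 1.1 points at 100 g fat. The protocol gives its protein figure as a minimum, so these intakes are not upper bounds.

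**Texts side by side, CFA change**

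| SAP section | Endpoint treated | Summary called for |
|---|---|---|
| 9.2.2 | CFA | comparison of mean CFAs; proportion with CFA ≥80%; values and change in *stool weights* |
| 9.3.1 | stool weight | change in stool weights |
| 9.3.3 | CNA | values and change in CNA |

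The sentence in 9.2.2 has the same form as the one in 9.3.3, with stool weights where CFA would be expected. Stool-weight change already has its own section.

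**The case against.** The strongest reply is that this is a copying slip whose intent is plain. The bullet still begins with nitrogen, the formula and listing agree with it, and the protocol has the dietitian calculate nitrogen (protein) intake. A competent programmer would use nitrogen. Read strictly, the rule cannot even be carried out, since no conversion exists, so the substitution illustrated above is not what the SAP instructs. It would also be easy to spot: fat and nitrogen consumed are both listed by patient and visit for about 12 patients, and nitrogen near 100 g/day would stand out.

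Most of that stands. It limits the likely harm and means the illustrated figures are no estimate of the real error. It does not make the rule right. An operative derivation in the governing analysis document should not need to be overridden.

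On 9.2.2, baseline CFA is an entry requirement and the mITT population requires a post-baseline CFA. Apart from values excluded because a patient switched back to PERT during collection, the mean change therefore equals the difference between the two means. What is missing is mainly the spread of the change, and the separate table specifications, not seen here, may supply it. That is why this part is only a minor slip.

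**Conclusion.** The concern holds. The CNA intake rule in SAP 9.3.3 is wrong as written and contradicts both its own section and Protocol 9.2.4.1. It should be corrected before programming. The consequence is confined to one secondary, descriptive endpoint; the primary endpoint values, the sample size and the error rates are untouched.

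The size of any error is unknown. If fat grams were used directly, a 4-point CNA difference would shrink to roughly 0.4 to 1.1 points over the accepted fat range, under the assumed body weights and the 6.25 factor and with CNA values from an earlier formulation. The textual finding does not depend on those assumptions.

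The 9.2.2 wording is a minor slip with no numeric error. The comparison of mean CFAs stands and individual changes are listed, but the SAP text does not call for a summary of within-patient CFA change.

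**What to change.** - **SAP 9.3.3:** replace fat consumption in the intake data point with the recorded 72-hour nitrogen (protein) intake, expressed per 24 hours. State the protein-to-nitrogen factor used, since intake may be supplied as protein while excretion is reported as nitrogen. The factor is useful detail; the correction does not depend on it.
- **SAP 9.2.2:** in the values-and-change sentence, replace stool weights with CFA, summarized in patients who have both values.
- **SAP 9.3.1:** extend the summary to values as well as change. The section now summarizes only the change, so the edit to 9.2.2 would otherwise drop the summary of stool-weight values.

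The cost is three short wording changes and one stated factor. Fat and nitrogen (protein) intake are already recorded, so no new data are needed. The separate table specifications should be checked against the corrected text.
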